## 166 *Outcomes and progression criteria:*

## 167 Feasibility outcomes:

1. Rate of participation  
Using the confidence interval approach, for a minimum sample size of 10 individuals, we estimate a rate of participation of 90% with a 95% confidence interval of +/- 18%.
2. Generation of an alert following abnormal vital signs (e.g. raised temperature).  
We aim for a minimum of 5 vital alerts to be generated to demonstrate feasibility.
3. Missing data recorded from sensor limited to less than 20% attrition will be a criterion for progression.
4. Number of adverse events relating to the sensor system (e.g., skin reaction to sensor preventing trial continuation)

178 Exploratory clinical outcomes:

1. Actions following alert generation (e.g., phone consultation, virtual general practitioner review, transfer to hospital).
2. Acceptability and usability of the SensiumVitals™ system by healthcare staff and participants (mixed methods analysis)

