89 Feasibility will be tested through rate of participation and number of vital alerts generated.

90 The SensiumVitals™ (Sensium Healthcare Ltd., United Kingdom) system can be engineered in the  
91 building (hotel) for use with the wearable sensor. All participants would be fitted with the sensor on  
92 arrival and would always be worn. A designated area within the facility would act as a central hub  
93 allowing for remote monitoring to occur by healthcare staff. Alerts would be generated, in  
94 accordance with NEWS parameters (Table 1) but can be individually tailored, to identify  
95 deteriorating participants. Participants can be escalated to hospitals should rapid deteriorating in  
96 vital signs be noted; ambulance services and paramedics will be present on site to facilitate this. The  
97 decision to escalate will come from a senior nurse, present on site, or a general practitioner  
98 contactable at all times.. The temperature alert threshold was lowered to the lowest score in the  
99 NEWS chart, allowing for earlier detection and improved sensitivity; this decision was made from  
100 previous work which demonstrated varying limits of agreement for temperature when compared to  
101 nursing observations. Escalation protocols will be developed and trialled, allowing staff to address  
102 issues as they arise (Figure 1).

103 *Wearable sensor system*  
104 SensiumVitals™ by the Surgical Company, have produced a lightweight, waterproof, single-use,  
105 wearable wireless ‘patch’ with a battery life of 5 days measuring vital signs every two minutes. The  
106 sensor attaches to an individual’s chest with two ECG electrodes, recording HR, RR, and a wire  
107 attaches around the individual’s back, measuring axillary temperature. The sensor is FDA approved  
108 and CE marked. Data are transmitted through radiofrequency and dedicated intranet hotspots.  
109 Physiological parameters can be viewed by clinical staff on a mobile device/desktop computer,  
110 allowing trends towards deterioration to be noted, with tailored alerts generated for deteriorating  
111 individuals in accordance with NEWS (Figure 2).

112 All sensor data collected by the SensiumVitals® system will be stored on a created secured hotel  
113 network; access to which is restricted to research personnel. Given that the hotel acts as an

114 extension to a healthcare trust, the SensiumVitals® system inherits all the hospital procedures and  

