## 198 Exclusion Criteria

- Any participants that withdraw their consent.
- A skin condition/reaction preventing wearing the wearable sensor (these can be communicated by the participant to the researcher or healthcare staff at the hotel).
- The presence of a permanent pacemaker or cardiac defibrillator.
- Any form of psychiatric disorder or a condition that, in the opinion of the investigator, may hinder communication with the research team.
- Inability to cooperate or communicate with the research team.

209 Descriptive statistics will be obtained about the baseline characteristics of participants. Continuous  
210 variables will be presented as mean  $\pm$  standard deviation or medians and ranges, depending on  
211 distribution. Categorical variables will be reported as numbers and percentages. The total  
212 frequencies of alerts, proportion of actioned alerts, and resultant actions will be described.  
213 Outcome measures (e.g. phone consultation, virtual GP review, transfer to hospital) will be reviewed  
214 from case notes should escalation occur and described in absolute frequencies. Questionnaire data  
215 will be presented using frequency distributions. Data will be analysed using SPSS, Stata, and  
216 GraphPad.

217 Qualitative analyses:

218 Semi structured interviews will take place by the primary lead researcher using the prepared topic  
219 guides. An audio recording will be made of all interviews. The interviewer may also take field notes  
220 reflecting the verbal responses and reflections to be used to adapt the topic/study direction. The  
221 audio recordings will be transcribed. The data will be analysed appropriately using thematic analysis.

222 To ensure confidentiality and anonymity, each interview will be allocated a pseudonym, to be  
223 applied to the corresponding consent form, topic guide form/field notes and audio file. Their name  
224 will not be included in the audio recording; the pseudonym will be used.

225 Summaries of interview field notes will be typed into a word processor. All paper and soft copies of  
226 field notes, audio files and consent forms will be kept securely in a locker within a locked office and  
227 if in digital format, on a password protected computer and backed up regularly. Information will only  
228 be shared within the study team.

229 Audio recordings will be professionally transcribed verbatim, and a random selection of transcripts  

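### The precision stated for participation (90% ± 18 points at n = 10) implies 72% to 108%; valid 95% intervals for 9 of 10 start at about 55% to 62%

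*Combined protocol and SAP*

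**What the plan says.** Under Outcomes and progression criteria, Feasibility outcomes, item 1, the plan gives its expected precision for the rate of participation: "for a minimum sample size of 10 individuals, we estimate a rate of participation of 90% with a 95% confidence interval of +/- 18" per cent. The sentence opens with "Using the confidence interval approach" and cites a source, but it names no interval method, prints no limits and does not mention truncation at 100%.

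Three other places bear on it:

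- Overall design (Methods) makes participation one of two measures of feasibility: "Feasibility will be tested through rate of participation and number of vital alerts generated".
- The descriptive statistics paragraph after the exclusion criteria plans no confidence interval for any result: "Categorical variables will be reported as numbers and percentages".
- Power considerations says that the available data do not support a power calculation. Item 1 is therefore the only quantitative precision statement tied to the minimum of 10.

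**The concern.** A symmetric margin of 18 points around 90% runs past 100%, so the interval cannot be right as written. Capping the upper end at 100% would remove the impossible value but leave the more important error at the lower end.

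A reader would conclude that observing 90% in 10 people puts a floor of 72% under the participation rate. In fact, 9 of 10 is compatible with a rate near 55% to 62%. The Discussion hopes that the results will help to power later randomised trials. A planner who took 72% as the plausible worst case would underestimate the recruitment risk.

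**Working it through.** **Inputs** (all from Feasibility outcomes, item 1): anticipated rate p = 0.90, minimum sample size n = 10, confidence level 95%, stated half-width 18 points. At n = 10 the anticipated rate is 9 of 10.

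**1. The interval as stated**

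0.90 − 0.18 = 0.72 and 0.90 + 0.18 = 1.08, so 72% to 108%.

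**2. Reproducing the plan's figure**

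The normal-approximation (Wald) half-width is z × √(p(1 − p)/n) = 1.96 × √(0.9 × 0.1/10) = 1.96 × 0.0949 = 0.186, or 18.6 points. The plan's 18 is this value with the decimal dropped; rounded, it would be 19. Other variants do not give 18:

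- one-sided z of 1.645: 15.6 points
- Wald with continuity correction: 23.6 points
- t with 9 degrees of freedom: 21.5 points

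The Wald formula is thus the likely source, but this is inferred because the plan does not name the method.

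**3. Accepted 95% intervals for 9 of 10**

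The Wilson interval can be followed by hand:

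- centre = (0.9 + 1.96²/20)/(1 + 1.96²/10) = 0.789
- half-width = [1.96/(1 + 1.96²/10)] × √(0.009 + 1.96²/400) = 0.193
- limits = 0.596 and 0.982

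The exact (Clopper-Pearson) lower limit is the rate at which 9 or more of 10 has probability 0.025, which is 0.555. The arms below are distances from 90%.

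| Interval | Limits | Lower arm (points) | Upper arm (points) | Total width (points) |
|---|---|---|---|---|
| As stated | 72% to 108% | 18 | 18 | 36 |
| Jeffreys | 61.9% to 98.9% | 28.1 | 8.9 | 37.0 |
| Mid-P | 59.7% to 99.5% | 30.3 | 9.5 | 39.8 |
| Wilson | 59.6% to 98.2% | 30.4 | 8.2 | 38.6 |
| Exact | 55.5% to 99.7% | 34.5 | 9.7 | 44.2 |

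The stated lower limit is too high by 72 − 61.9 = 10.1 points (Jeffreys) to 72 − 55.5 = 16.5 points (exact). Less common methods widen the range of lower limits slightly, from 53.3% (logit) to 62.8% (likelihood ratio). All stay well below 72%.

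**4. Direct check on rates below 72%**

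The binomial probability of 9 or more of 10 is 8.6% if the true rate is 65% and 14.9% if it is 70%. Both exceed 2.5%, so neither rate is excluded at the two-sided 95% level.

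**5. Coverage of the Wald interval**

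With n = 10 and a true rate of 90%, the Wald interval contains 90% only when 6, 7, 8 or 9 people participate. The probabilities are 0.011 + 0.057 + 0.194 + 0.387 = 0.650 (summed before rounding), so coverage is about 65%, not 95%. Most of the loss comes from 10 of 10 (probability 0.349), where the interval collapses to the single point 100%.

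**6. Denominator**

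The plan does not say whether the 10 are people approached or people enrolled. If 10 enrol out of 11 approached (an assumption), the lower limits are 64.7% (Jeffreys), 62.3% (Wilson) and 58.7% (exact), still below 72%.

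**The case against.** The strongest reply is that the plan states a planning half-width, not limits, and that this half-width is nearly right. It follows from a standard formula. The total width of 36 points is close to 37.0 (Jeffreys) and 38.6 (Wilson); only the exact interval, at 44.2, is clearly wider. On this view the fault lies in the choice of method rather than in the arithmetic. It also changes no decision: no participation threshold is set, the results are to be described only as counts and percentages, and 10 is a minimum in a study meant to run for the duration of the pandemic. The cited source for the approach is not available to check.

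Much of this stands. The error is mainly one of position: the lower arm is too short and the upper arm too long. The limits of 72% and 108% are implied, not printed, and no progression rule would change. None of it makes the sentence correct, though. A ± margin around 90% has no other plain reading, neither a formula nor a citation can make an upper limit above 100% valid, and near-correct width does not repair a lower limit 10 to 17 points too high.

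**Conclusion.** The concern holds. The stated interval is impossible at its upper end and, against four accepted methods, about 10 to 17 points too optimistic at its lower end. The conclusion does not depend on which of these methods is preferred, nor on whether the denominator is 10 or, by assumption, 11. It rests on reading the anticipated 90% as 9 of 10 and the interval as two-sided 95%.

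The practical consequence is modest, because no go/no-go rule uses the interval. It should still be corrected, since it misstates the precision of a named feasibility measure.

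**What to change.** Restate item 1 of the feasibility outcomes along these lines: if 9 of 10 individuals participate (90%), the 95% confidence interval is 60% to 98% (Wilson). If the exact method is preferred, the limits are 55.5% to 99.7%. Choose one method and name it. Say in the same sentence whether the 10 are people approached or people enrolled, so that the denominator is clear.

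In the descriptive statistics paragraph, add that the observed participation rate will be reported with that same interval. The change can be confined to the participation rate.

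The cost is one sentence restated and one short addition. No extra participants or data are needed, and the sample size stays as it is. The only downside is a less favourable statement of precision.

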# Design of the pilot, proof of concept REMOTE-COVID trial: REmote MOniToring usE in suspected cases of COVID-19 (SARS-CoV 2)

## A trial protocol

[name]1\*, [name], [name], [name], [name], [name]

- 1) Division of Surgery & Cancer, [name]
- 2) West Middlesex University Hospital, [name]

Clinical trials registration information: ClinicalTrials.gov Identifier: NCT04337489

16 March 2020

16 Abstract:

17 Background: The outbreak of SARS-CoV-2 (coronavirus, COVID-19), declared a pandemic by the  
18 World Health Organisation (WHO) is global health problem with ever-increasing attributed deaths.  
19 Vital sign trends are routinely used to monitor patients with changes in these parameters often  
20 preceding an adverse event. Wearable sensors can measure vital signs continuously (e.g. heart rate,  
21 respiratory rate, temperature) remotely and can be utilised to recognise early clinical deterioration.

22 Methods: We describe the protocol for a pilot, proof-of-concept, observational study to be  
23 conducted in an engineered hotel near London airports, United Kingdom. The study is set to  
24 continue for the duration of the pandemic. Individuals arriving to London with mild symptoms  
25 suggestive of COVID-19 or returning from high risk areas requiring quarantine, as recommended by  
26 Public Health England, or healthcare professionals with symptoms suggestive of COVID-19 unable to  
27 isolate at home will be eligible for a wearable patch to be applied for the duration of their stay.  
28 Notifications will be generated should deterioration be detected through the sensor and displayed  
29 on a central monitoring hub viewed by nursing staff, allowing for trend deterioration to be noted.  
30 The primary objective is to determine the feasibility of remote monitoring systems in detecting  
31 clinical deterioration for quarantined individuals in a hotel.

32 Discussion: This trial should prove the feasibility of a rapidly implemented model of healthcare  
33 delivery through remote monitoring during a global pandemic at a hotel, acting as an extension to a  
34 healthcare trust. Potential benefits would include reducing infection risk of COVID-19 to healthcare  

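### The five-alert feasibility aim is a raw study-wide count with no counting rule, no exposure base and no denominator of abnormal episodes

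*Combined protocol and SAP*

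**What the plan says.** Under Outcomes and progression criteria, item 2 of the feasibility outcomes is the generation of an alert after abnormal vital signs. Its target reads: "We aim for a minimum of 5 vital alerts to be generated to demonstrate feasibility". Methods, Overall design, gives this count a formal role: "Feasibility will be tested through rate of participation and number of vital alerts generated". In the Abstract, "The primary objective is to determine the feasibility of remote monitoring systems in detecting" clinical deterioration, and the first hypothesis is that monitoring will identify deteriorating patients.

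Other parts of the plan that bear on the count:

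- **Trigger.** Table 1 sets default limits for respiratory rate, temperature and heart rate. Overall design allows the limits to be tailored to the individual.
- **Readings.** The patch is described as "with a battery life of 5 days measuring vital signs every two minutes" (Wearable sensor system).
- **Size and duration.** The feasibility outcomes give a minimum of 10 individuals and no maximum. The study is to "continue for the duration of the pandemic" (Abstract). Background says a two-week quarantine may be required. The Discussion accepts that travel restrictions could change the sample size considerably.
- **Who is monitored.** The inclusion criteria admit people with mild symptoms and also travellers who only need quarantine after a high-risk area.
- **Analysis.** The descriptive-statistics paragraph plans alert totals, the proportion of alerts actioned and the resulting actions.

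**The concern.** The outcome is conditional: given an abnormal sign, was an alert raised? The target is unconditional: were there five alerts in all? Three things needed to connect them are absent.

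1. **Counting unit.** Nothing says when successive readings over a limit form one alert, or when a repeat counts as new.
2. **Exposure base.** No rate per participant-day is planned, although the number of participants and the length of stay are both open.
3. **Denominator.** Abnormal episodes that raised no alert are not counted anywhere. The planned proportion actioned starts from alerts already raised, so it cannot reveal them.

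At stake is what the result can support. Followed as written, the rule can declare feasibility whatever share of abnormal episodes produced an alert. It can also fail a fully working system because the cohort was small or well.

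**Working it through.** **1. The plan's own figure.** The documents give no alert rate, person-time or episode count behind the number 5, and Power considerations says the data for a power calculation do not exist. The figure cannot be reproduced.

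**2. Counting unit (documents only).** Readings come every 2 minutes. Five consecutive readings have 4 intervals: 4 × 2 = 8 minutes. One such run in one participant may be read as five alerts (aim met) or as one.

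**3. Five alerts as a rate.** With assumed 14-day stays, five alerts are 5/(10 × 14) = 3.57 per 100 participant-days at n = 10, but 5/(100 × 14) = 0.36 at n = 100. The same count stands for a tenfold difference in rate.

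**4. Chance of meeting the aim.** Let X be the number of alert episodes, Poisson with mean μ = rate × days × n × delivery, where delivery is the share of abnormal episodes that raise an alert. Assumptions, none of them from the documents: 0.02 episodes per participant-day, 14 days for everyone, delivery 1 or 0.5. Only n = 10 is a plan figure.

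| n | Full delivery: μ | P(X ≥ 5) | Half delivery: μ | P(X ≥ 5) |
|---|---|---|---|---|
| 10 | 2.8 | 0.15 | 1.4 | 0.014 |
| 20 | 5.6 | 0.66 | 2.8 | 0.15 |
| 40 | 11.2 | 0.99 | 5.6 | 0.66 |
| 100 | – | – | 14.0 | 0.998 |

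Along a row, the count does respond to delivery. Across rows, half delivery in 40 participants (0.66) meets the aim far more often than full delivery in 10 (0.15).

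**5. Range over the assumed rate.** Full delivery at n = 10 against half delivery at n = 40:

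- 0.01 per day: μ = 1.4 against 2.8, probability 0.014 against 0.15.
- 0.05 per day: μ = 7.0 against 14.0, probability 0.83 against 0.998.

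The ordering is the same at each rate.

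**6. Clustering within participants.** Take a negative binomial count per participant with mean m = 0.02 × 14 = 0.28 (full) or 0.14 (half), variance m + m²/k, and assumed k = 0.2, so the total has size 0.2n. For n = 10, 20 and 40, P(X ≥ 5) is 0.21, 0.56 and 0.93 with full delivery, and 0.05, 0.19 and 0.59 with half. Full at 10 (0.21) is still below half at 40 (0.59).

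**7. What five alerts say about delivery.** This step needs no episode rate. Exact (Clopper-Pearson) 95% intervals:

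- 5 of 5 episodes: 100% (48–100%)
- 5 of 10: 50% (19–81%)
- 5 of 20: 25% (9–49%)

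The aim is met in all three cases.

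**The case against.** The strongest reply is that this is a proof-of-concept pilot and the number is worded as an aim. Only item 3 is expressly a progression rule: "Missing data recorded from sensor limited to less than 20% attrition will be a criterion for progression". Overall design also states the objective as the feasibility of delivering care remotely in a hotel, and a modest yield of alerts handled suits that. All of this is fair, and it limits the weight of the point. It does not remove it: Overall design names the alert count as a test of feasibility, item 2 says what the five alerts are meant to demonstrate, and the first hypothesis concerns identifying deterioration.

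A second reply is that half delivery is hypothetical. If episodes were missed because readings were lost, the missing-data limit would probably show it, and any minimum count becomes easier to reach as n grows. The first part stands for lost readings. It does not cover readings that were received but raised no alert at the hub. The second part is the concern itself, since n has no ceiling.

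A third reply is that the natural unit is whatever alert the system issues. That is a reasonable reading, but the text does not state it or say when a repeat is issued. Figures 1 and 2 could not be seen; their legends describe the escalation pathway and the monitoring display, not a counting rule.

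**Conclusion.** The concern holds. The aim has no defined unit, no exposure base and no denominator. Five alerts can show that the escalation pathway was exercised; they are not by themselves evidence that monitoring detects deterioration.

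The 8-minute example follows from the documents, and the delivery intervals need no assumed episode rate, though they treat episodes as independent. The pass probabilities rest on the assumed episode rates, 14-day stays, delivery shares and cohort sizes. They illustrate the mechanism and do not forecast this trial. The point should be fixed, but it is bounded: the target is an aim, it is one of four feasibility outcomes, and at a fixed n the count does carry some information about delivery.

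**What to change.** Keep five alerts only as a minimum yield for trialling the escalation pathway, and say that it is not in itself evidence of detection. For analysis only, with no change to live alerting, define an alert episode by merging consecutive exceedances in one participant under a rule fixed in advance. Then report:

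1. Alert episodes per 100 participant-days, with the participant-days and the number of participants contributing. This deals with exposure but not with illness mix.
2. The proportion of episodes crossing the limits in force for that participant that generated a hub alert, with an exact 95% interval. Label it alert delivery, not accuracy. Note that the interval ignores clustering by participant and that episodes lost to missing readings drop out of it, so read it beside the missing-data result. If no episodes occur, report delivery as not assessable, not as failed.
3. From the record review already planned under Sequence of events, item 6, the number of hospital transfers that did and did not follow an alert.

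The cost is protocol wording, a little extra analysis of sensor data and records already to be obtained, a dated log of tailored limits if none is kept, and the loss of a simple count as a pass mark.

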## 184 *Participant eligibility:*

185 The study will recruit flight arrivals returning to the UK in London. High risk travellers are screened  
186 at the airport and tested for COVID-19, with transfer to hospital if appropriate; this cohort would be  
187 ineligible for the study.

188 Additionally, healthcare professionals who display symptoms of COVID-19 and are unable to isolate  
189 safely at home (e.g. lodging with vulnerable persons) would be eligible to take part in the study and  
190 invited to stay at the hotel.

